2.4.3 Extent of investigational medicinal product exposure and compliance

The extent of IMP exposure and compliance in the open-label period will be assessed and summarized by actual treatment (placebo/teriflunomide, teriflunomide/teriflunomide and overall treatment group) within the safety population ([Section 2.3.3](#)).

2.4.3.1 Extent of investigational medicinal product exposure

The extent of IMP exposure will be assessed by the duration of IMP exposure in the open-label period of the study.

Duration of open-label IMP exposure is defined as last dose date of teriflunomide - first dose date of teriflunomide +1 day in the open-label period, regardless of unplanned intermittent discontinuations (see [Section 2.5.2](#) for calculation in case of missing or incomplete data).

Duration of open-label IMP exposure will be summarized descriptively as a quantitative variable (number, mean, SD, median, minimum, and maximum). In addition, duration of treatment exposure will also be summarized categorically by numbers and percentages for each of the following categories and cumulatively according to these categories: >0 to ≤4 weeks, >4 to ≤12 weeks, >12 to ≤24 weeks, >24 to ≤48 weeks, >48 to ≤72 weeks, >72 to ≤96 weeks, >96 to ≤120 weeks, >120 to ≤144 weeks, >144 to ≤168 weeks, >168 to <192 weeks and ≥192 weeks. The number and percentage of patients by final open-label IMP dose and by dose at the end of PK

run-in of the open-label period will also be presented by each treatment group. A list of the patients who changed dose after the end of the PK run-in of the open-label period will be provided. The number and percentage of patients with each open-label IMP dose level by visit and with dose increase/decrease/unchanged by visit will also be presented by each treatment group if necessary. Cumulative exposure of the IMP taken in the double-blind and open-label treatment periods will be summarized with descriptive statistics from the first dose of IMP in the double-blind period to the last dose of IMP in the open-label period for each treatment group.

2.4.3.2 Compliance

A given administration will be considered noncompliant if the patient did not take the planned dose of treatment as required by the protocol. No imputation will be made for patients with missing or incomplete data.

Percentage of compliance for a patient will be defined as the number of administrations that the patient was compliant divided by the total number of administrations that the patient was planned to take during the treatment epoch defined in [Section 2.1.4](#).

Above-planned dosing percentage for a patient will be defined as the number of administrations that the patient took a higher dose than planned divided by the total number of administrations that the patient was planned to take during the treatment epoch.

Under-planned dosing percentage for a patient will be defined as the number of administrations that the patient took a lower dose than planned divided by the total number of administrations that the patient was planned to take during the treatment epoch.

Treatment compliance, above-planned, and under-planned dosing percentages will be summarized descriptively as quantitative variables (number, mean, SD, median, minimum, and maximum). The percentage of patients whose compliance is <80% will be summarized. In addition, numbers and percentages of patients with at least 1 above-planned dose administration will also be provided, as well as numbers and percentages of patients with 0, (0, 20%], and >20% under-planned dose administrations.

In order to address impact of the Covid-19 pandemic, Covid-19 impacted compliance summary will be provided based on safety population including but not limit to the below items.

- Number of patients who used Direct-to-patient (DTP)
- Number of patients who did not compliant to the protocol IMP administration due to the Covid-19 (e.g. dose interruption, dose prolongation, etc.)
- Number of patients who had dose interruption due to the Covid-19
- Duration of non-compliant period due to the Covid-19
- Duration of dose interruption period due to the Covid-19.

Treatment compliance will also be summarized by group (3.5 mg, 7 mg, and 14 mg teriflunomide at the end of PK run-in phase of the open-label period) and baseline body weight (≤ 40 , >40 kgs).

2.4.4 Analyses of efficacy endpoints

All the following efficacy analysis will be conducted on efficacy population, according to the treatment group allocated by randomization in the double-blind period (ie, placebo/teriflunomide versus teriflunomide/teriflunomide). Baseline values of the double-blind period will be used as the baseline in the efficacy analysis for the open-label CSR, unless otherwise noted.

Analyses of efficacy endpoints of the open-period period are of exploratory intent in principle. Long-term treatment effects and the 95% confidence intervals, where applicable, will be assessed since the randomization date in the double-blind period throughout the last visit of the open-label period of the study; unless otherwise noted. P-values will be provided if applicable. No confirmative conclusion should be drawn based on p-value because of exploratory nature of open-label period analysis.

2.4.4.1 Analysis of primary efficacy endpoint

Clinical relapses are defined as new or recurrent neurological symptoms not associated with fever or infection, lasting at least 24 hours, and accompanied by new objective neurological findings upon examination by the Examining Neurologist and documented by the Functional System Scores (FSS). New or recurrent symptoms that occur less than 30 days following the onset of a relapse are considered part of the same relapse.

Note that the process of confirmation of clinical relapse is different between the double-blind period and the open-label period. Confirmation in the double-blind period involves the Relapse Adjudication Panel (RAP), whereas confirmation in the open-label period is done by the investigative center. However, some analyses will combine confirmed relapses from both treatment periods, as the criteria used in the two processes are similar.

The first clinical confirmed relapse occurring from randomization in the double-blind period (including relapses during the PK run-in (8 weeks) phase) to the end of the open-label period will be included for analysis. Treatment effect as measured by the hazard ratio and its associated 95% confidence interval will be estimated using a Cox proportional-hazards model with robust variance estimation (1). Cox model will include factors for treatment group, region, pubertal status, age, and number of relapses in the year prior to randomization. The duration of time to the event will be included in the modeling to offset the lengths of individual observations. Kaplan-Meier estimates of probability of clinical relapse at Week 24, 48, 72, 96, 120, 144, 168 and 192 will be estimated. The complementary log-log transformation will be used to construct 95% confidence intervals. A Kaplan-Meier survival curve from randomization in double-blind period to the end of open-label period will be presented. A stratified log-rank test with time to first clinical relapse as the dependent variable, treatment group as a test variable, region (definition of the regions are provided in [Section 2.5.5](#)), and pubertal status as covariates will be provided as supportive.

Censoring rule

If a patient has no clinical relapse after randomization in double-blind period and before treatment discontinuation/completion in the open-label period, the patient will be considered as free of relapse till the date of last IMP administration reported on the EOT page. If this date is missing, last dose date on the IMP administration page will be used.

Given that confirmation of relapse in the open-label period is based on objective neurological examinations, it is possible that a patient remained on treatment but did not perform any objective neurological examinations due to Covid-19 pandemic. If a patient reported suspected MS relapse and had no objective neurological examinations assessed afterwards due to the pandemic, the censor date will be the date of the last EDSS or FSS assessment.

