2.1.3.1 Primary efficacy endpoint(s)

The primary efficacy endpoint is the time to first clinical relapse after randomization up to end of double-blind treatment period, which is not directly applicable for the open-label treatment period since Relapse Adjudication Panel (RAP) of the double-blind period was not continued into the open-label period. Refer to the SAP for the double-blind period of the study.

However, time to first clinical relapse after randomization in double-blind period up to the end of the open-label treatment period will be performed on relapses with objective signs on the Examining Neurologist's examination (which is the basis for RAP confirming relapses) as a primary efficacy endpoint for analysis period from randomization to the end of the open-label period.

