2.1.4 Safety endpoints

The safety analysis will be based on the reported adverse events and other safety information, such as clinical laboratory data, vital signs, ECG, etc.

Observation period

The observation period of the open-label period will be divided into 3 epochs:

- The **treatment** epoch is defined as the time from the first administration of the IMP in the open-label period to the last administration of the IMP in the open-label period.
- The **accelerated elimination** epoch is defined as the time from 1 day after the open-label treatment epoch up to 4 weeks (28 days) after the last administration of the IMP in the open-label period or up to the first administration in optional additional extension period, whichever occurs first.

The treatment-emergent adverse event (TEAE) period will include both treatment and accelerated elimination epochs.

- The **posttreatment** epoch is defined as the period of time starting from the day after the end of the treatment-emergent adverse event period up to the end of the open-label period (defined as the first dose of optional additional extension IMP for patients enter optional additional extension period, or the last protocol-planned visit, EOT +4W, in the open-label period or the resolution/stabilization of a followed-up AE for patients do not enter).

The on-study observation period is defined as the combination of TEAE period and posttreatment epoch.

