2.4.4.2 Analyses of secondary efficacy endpoints

2.4.4.2.1 Time to first clinical relapse after enrollment of open-label period up to the end of open-label period

The first clinical relapse occurring from enrollment of open-label period to the end of the open-label period will be included for analysis. Hazard ratio with associated 95% confidence interval, Kaplan-Meier estimates and its 95% confidence interval will be presented using the same method as described in [Section 2.4.4.1](#). A stratified log-rank test with time to first clinical relapse as the dependent variable, treatment group as a test variable, region (definition of the regions are provided in [Section 2.5.5](#)), and pubertal status as covariates will be provided.

Censoring rule

If a patient has no clinical relapse after enrollment in open-label period and before treatment discontinuation/completion in the open-label period, the patient will be considered as free of relapse till the date of last IMP administration reported on the EOT page. If this date is missing, last dose date on the IMP administration page will be used.

Given that confirmation of relapse in the open-label period is based on objective neurological examinations, it is possible that a patient remained on treatment but did not perform any objective neurological examinations due to Covid-19 pandemic. If a patient reported suspected MS relapse and had no objective neurological examinations assessed afterwards due to the pandemic, the censor date will be the date of the last EDSS or FSS assessment.

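### The open-label relapse analyses count events to the end of the open-label period but censor at last dose, so a first relapse in between is an event under one sentence and censored under the next

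*SAP*

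**What the plan says.** **Event rule.** SAP 2.4.4.1 takes the first confirmed relapse from randomization "to the end of the open-label period will be included for analysis". SAP 2.4.4.2.1 does the same from open-label entry: "The first clinical relapse occurring from enrollment of open-label period to the end of the open-label period will be included for analysis".

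**Where the period ends.** SAP 2.1.4 gives the explicit definition. For patients who go on to the optional extension, the end is "defined as the first dose of optional additional extension IMP for patients enter optional additional extension period". For everyone else it is "the last protocol-planned visit, EOT +4W, in the open-label period or the resolution/stabilization of a followed-up AE".

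**Censoring rule.** In both sections, a patient with no clinical relapse "before treatment discontinuation/completion in the open-label period" is censored: "the patient will be considered as free of relapse till the date of last IMP administration reported on the EOT page".

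**Endpoint definition.** SAP 2.1.3.1 defines the endpoint "up to the end of the open-label treatment period", but the same sentence closes by naming the open-label period, without the word treatment, as the analysis period. SAP 2.1.3.2, the first relapse bullet of Section 3, and Appendix B refer to the treatment period.

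**Neighbouring endpoint.** For the annualized relapse rate, SAP 2.4.4.3.1 ends both the relapse count and the time at risk at last dose, and equates the date of treatment discontinuation or completion with the last intake date.

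**The concern.** A time-to-event endpoint needs one cut-off that governs both which events count and when event-free patients leave the risk set. Here the inclusion sentence and the censoring rule use different dates, and the interval between them is off-drug for patients who stop teriflunomide. Protocol 9.9 prescribes an accelerated elimination procedure for them.

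Two programmers could follow the text and reach different event counts. If the inclusion sentence prevails, a patient who relapses two weeks after last dose is an event, while a patient followed just as long without relapse is removed at last dose. The post-dose interval then supplies events but no event-free follow-up. The relapse endpoints and the annualized relapse rate in the same report would also rest on different sets of relapses.

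**Working it through.** **1. The rules side by side.** Take a patient who does not enter the extension and whose first relapse starts 14 days after the last open-label dose.

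- Inclusion sentence (2.4.4.1, 2.4.4.2.1, with the period end from 2.1.4): day 14 is before the four-week visit, so this is an event.
- Censoring rule (same sections): there was no relapse before discontinuation or completion, so the patient is relapse-free and censored at last dose.
- Annualized relapse rate (2.4.4.3.1): onset is after last intake, so the relapse is not counted.

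For disability progression, SAP 2.4.4.3.2 says how EDSS values after treatment are used. There is no such statement for relapse.

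**2. Can such relapses be recorded?** Yes. Protocol 10.3.2 asks patients who stop permanently to continue visits that include relapse reporting, and the flow charts provide an unscheduled relapse visit.

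**3. Reproducing the plan's hazards (SAP 1.3).** A 60% two-year placebo relapse rate gives −ln(0.40)/2 = 0.4581 per year. Half of that is 0.2291. The teriflunomide two-year rate is 1 − exp(−2 × 0.2291) = 36.8%. All three agree with the SAP.

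**4. Chance of a first relapse in the gap.** The gap is taken as 28 days, the length of the accelerated elimination epoch in SAP 2.1.4.

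- Teriflunomide hazard: 1 − exp(−0.2291 × 28/365.25) = 1.74%.
- Placebo hazard: 1 − exp(−0.4581 × 28/365.25) = 3.45%.

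**5. How many are still relapse-free at Week 192?** Assume all 165 enter open label and stay, and that placebo patients take the teriflunomide hazard after Week 96. Week 192 is 192 × 7/365.25 = 3.68 years; Week 96 is 1.84 years.

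- Teriflunomide/teriflunomide: exp(−0.2291 × 3.68) = 0.430, or 47.3 of 110.
- Placebo/teriflunomide: exp(−0.4581 × 1.84 − 0.2291 × 1.84) = 0.282, or 15.5 of 55.
- Together about 63 relapse-free, and 165 − 63 = 102 with an earlier event.

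**6. Patients whose status depends on the rule.** 63 × 1.74% = 1.1 and 63 × 3.45% = 2.2, so about 1 to 2. The extreme case, with all 165 relapse-free at last dose, gives 165 × 1.74% = 2.9 to 165 × 3.45% = 5.7.

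**7. Direction and place of the effect.** Each event multiplies the Kaplan-Meier curve by (1 − d/n). Counting a post-dose relapse raises d, while n has already lost every relapse-free patient at last dose. The estimated relapse probability can therefore only rise. Timed from randomization, completers stop near Week 192, so a later relapse falls where n is very small and shows mainly in the tail of the plotted curve. Timed from open-label entry, durations run from 96 to 184 weeks (Protocol 5.1 and the flow-chart notes). A post-dose relapse can then fall well inside the curve, so this endpoint is more exposed.

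**The case against.** The strongest reply is that the SAP treats the two phrases as synonyms. SAP 2.1.3.1 uses both in one sentence, and SAP 1.1 lists the four-week follow-up as a component separate from the open-label period. The longer definition sits in a safety section that the efficacy sections do not cite. On this view the censoring rule is operative and nothing is ambiguous.

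That does not hold up. SAP 2.1.2 runs follow-up medications from the day after last intake to the end of the open-label period, which requires the period to outlast treatment. Note c to Table 7 ends it at the later of the last open-label visit or before the first extension dose. What does stand is the inference about intent: most of the endpoint wording and the annualized relapse rate point to last dose, so the inclusion sentences are the ones to correct.

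The reply is also right about size. Patients entering the extension may have almost no gap. Those moving directly to commercial product need no post-elimination visits (Protocol 10.1.4). No EDSS is scheduled at the two- and four-week follow-up visits, so detection depends on an unscheduled visit. From randomization, the reported estimates up to Week 192 are touched mainly by early stoppers. If the planned 20% two-year dropout (0.1116 per year) continued alongside the teriflunomide hazard, 0.1116/0.3407 × [1 − exp(−0.3407 × 3.68)] = 23% would stop relapse-free. That is about 39 of 165, and 0.7 to 1.3 relapses in their 28-day gaps.

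**Conclusion.** The contradiction is in the text and is not resolved elsewhere. It affects only patients whose first relapse falls between last open-label dose and the end of the period: about 1 to 2 patients against about 102 earlier events. That count rests on the planning hazards, a 28-day gap and full entry and retention of 165 patients. The gap can be longer where it ends at resolution of an adverse event.

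Three stronger readings are not supported.

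- A reader might infer that the estimates are biased as planned. The bias arises only if post-dose relapses are counted, and the censoring rule says they are not.
- A reader might expect many more events because early stoppers are followed to Week 96. Under SAP 2.1.4 the period normally ends four weeks after end of treatment, so most of that follow-up lies outside the window. It also applies only to patients who stop within 96 weeks of randomization (Protocol 10.1.3.4).
- A reader might think the trial's main conclusion is at risk. SAP 2.4.4 and 2.4.4.4 declare the open-label efficacy analyses exploratory, and the powered double-blind comparison does not use this window.

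The point is worth correcting because it concerns event status in the endpoint that this SAP calls primary, and because the remedy is nearly free.

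**What to change.** In SAP 2.4.4.1 and 2.4.4.2.1, define the event as a first clinical relapse with onset on or before the last open-label IMP date. This matches the censoring rules, the treatment-period wording in 2.1.3.1, 2.1.3.2 and Appendix B, and the annualized relapse rate.

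Align the remaining references to the end of the open-label period: the close of the sentence in 2.1.3.1, the Kaplan-Meier curve sentence in 2.4.4.1, the heading of 2.4.4.2.1, and the second relapse bullet of Section 3. The general statement in 2.4.4 about assessing effects through the last visit allows exceptions and can stay.

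List relapses with onset after last dose separately by treatment group. The cost is a handful of wording changes and one listing; no data collection or other analysis changes.

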### **11.4.4 Analyses of efficacy endpoints**

#### **11.4.4.1 Analysis of primary efficacy endpoint(s)**

##### **Main statistical model and adjustment for covariates:**

Time to first relapse will be analyzed using a log-rank test with time to first relapse as the dependent variable, treatment group as a test variable, and region and pubertal status as covariates. The first RAP confirmed relapse, occurring from randomization (including relapses during the PK run-in (8 weeks) phase) to the end of the randomized, placebo-controlled study treatment period, will be included for analysis. Treatment effect as measured by the hazard ratio and its associated 95% confidence interval will be estimated using a Cox proportional-hazards model with factors for treatment group, region, pubertal status, age, and number of relapses in the year prior to randomization. Statistical significance will be claimed for the primary endpoint if the p-value for the 2-sided log-rank test is  $\leq 0.05$ .

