2.4.4.2.3 Magnetic resonance imaging (MRI) variables

General rules for MRI variables

The protocol requires that the MRI should not be performed until after a minimum of 14 days following completion of corticosteroid therapy. Thus, MRI values obtained within 14 days of systemic corticosteroid therapy will be excluded from the analysis.

Baseline for MRI variables is defined as the last non-missing, valid MRI value that was measured before or on the day of first administration of IMP in the double-blind period. A previous MRI performed in the 6 weeks preceding randomization could be used as the baseline if performed according to the specifications for this study. For valid MRI values in subsequent post baseline visits, time windows (see [Table 4](#) and [Table 5](#) in [Section 2.5.3](#)) between visits will be used to capture MRI measurements. For multiple records within a visit window, the one closest to the targeted visit date will be used.

Number of lesions

The number of new or enlarged T2 lesions per MRI scan will be analyzed using a negative binomial regression model with robust variance estimation. The model will include the total number of new or enlarged T2 lesions as the response variable, with treatment group, region, pubertal status and age as covariates. In order to account for different numbers of MRI scans performed among patients, the log-transformed number of scans will be included in the model as an offset variable. The robust error variances can be estimated by specifying the patient identifier in the repeated statement using SAS PROC GENMOD. The estimated number of lesions per scan and associated 2-sided 95% confidence interval (CI) will be provided for each treatment group.

The number of T1 Gd-enhancing lesions per MRI scan and the number of new T1 hypointense lesions per MRI scan will be analyzed using a similar negative binomial regression model as described above for T2 lesions.

Volume of lesions and brain

Descriptive statistics of the change from baseline in volume of T2 lesions, T1 hypointense lesions and the percentage change of brain volume in the original scale will be summarized at each visit by treatment group.

The proportion of patients free of new or enlarged T2 lesions

The proportion of patients free of new or enlarged T2 lesions at Weeks 48, 96, 144 and 192 will be summarized based on all patients having an MRI at these time points. Kaplan-Meier methods will be used for estimation.

Censoring rule

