Adjusted ARR will be performed using a Poisson regression model with robust error variance that would accommodate the potential over-dispersed data appropriately. The model will include the total number of clinical relapses as the response variable, treatment group as the test variable, pubertal status, and region as covariates. In order to account for different treatment durations among subjects, the log-transformed standardized treatment duration will be included in the model as an “offset” variable for appropriate computation of relapse rate. The robust error variances can be estimated by specifying the patient identifier in the repeated statement using SAS PROC GENMOD, and this is equivalent to the Generalized Estimating Equation (GEE) model. In comparison to the regular Poisson model, the GEE estimator is robust against

violation of the correlation structure and the distributional assumptions. The treatment-by-strata and treatment-by-region interactions will be evaluated separately at the 5% level of significance by adding the corresponding interaction term to the model. If a statistically significant interaction is detected at $p < 0.05$, further investigations will be performed for the possibility of qualitative interaction.

The estimated relapse rates and 2-sided 95% confidence intervals will be provided for each treatment group. Nelson-Aalen mean cumulative function plot will be provided for descriptive purposes.

2.4.4.3.2 *Time to sustained disability progression (using EDSS)*

The time to sustained disability progression will be assessed by EDSS during the study. The first disability progression (ie, confirmed disability worsening) is defined as a sustained increase of at least 1.0 point (0.5 for subjects with baseline EDSS > 5.5) persisting for at least 24 weeks from baseline EDSS in the double-blind period of the study.

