- If a patient has no EDSS increase that meets the criteria for progression before treatment discontinuation/completion, then the patient will be considered as free of progression till the date of last during-treatment EDSS evaluation.
- If a patient has an EDSS increase that meets the criteria for progression before treatment discontinuation, all available EDSS assessments obtained during the follow-up visits will be used to serve the purpose of progression confirmation. The patient will be considered as having disability progression if the first increase during treatment period is confirmed for at least 24 weeks during the follow-up visits. If the EDSS from the follow-up visit(s) does not confirm a sustained increase or despite all possible attempts, no confirmatory EDSS assessment is obtained after withdrawal, the patient will be considered as free of disability progression until the date of last during treatment EDSS evaluation.
- If a patient has an EDSS increase that meets the criteria for progression and completes the treatment period before the progression can be confirmed, then the patient will be considered as free of progression till the date of last during-treatment EDSS evaluation.
- In rare cases, if a patient had a delayed EDSS scheduled during the open-label period but performed during the optional extension period due to the Covid-19 pandemic, then this assessment will still be considered as during-treatment EDSS evaluation. The delayed EDSS result will be considered in the sustained disability progression determination process in the open-label analysis.
- In rare cases, if a patient had a delayed EDSS scheduled during the open-label period but performed after treatment discontinuation due to the Covid-19 pandemic, then the delayed EDSS result will be used for progression confirmation purpose only.

The hazard ratio and 95%CI for teriflunomide/teriflunomide versus placebo/teriflunomide will be estimated using Cox regression model with treatment group, region and baseline pubertal status as covariates, offset by the lengths of individual observations.

The Kaplan-Meier method will be used to estimate median time (if possible) to disability progression sustained for at least 24 weeks and cumulative disability progression rates specific to each treatment group. Kaplan-Meier graphs will be generated; quartiles and point probabilities will be calculated. Interval estimates will be calculated using 95% point wise confidence intervals.

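### The open-label SAP offsets its Cox models by each patient's own observed time; followed literally, this biases the exploratory hazard ratios

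*SAP*

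**What the plan says.** SAP Section 2.4.4.1 covers time to first clinical relapse from randomization to the end of the open-label period. The hazard ratio is to be "estimated using a Cox proportional-hazards model with robust variance estimation", with factors for treatment, region, pubertal status, age and prior-year relapses. The next instruction is: "The duration of time to the event will be included in the modeling to offset the lengths of individual observations".

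The same device reaches the other two Cox analyses:

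- Section 2.4.4.2.1 (relapse after open-label enrollment) takes it over by cross-reference to Section 2.4.4.1: "Kaplan-Meier estimates and its 95% confidence interval will be presented using the same method as described in".
- Section 2.4.4.3.2 (sustained disability progression) writes it into the model specification: "region and baseline pubertal status as covariates, offset by the lengths of individual observations".

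None of the three gives a transformation, a time unit or a sign. The two count models do give one. For MRI lesions (Section 2.4.4.2.3), "the log-transformed number of scans will be included in the model as an offset variable". For annualized relapse rate (Section 2.4.4.3.1), "the log-transformed standardized treatment duration will be included in the model as an" offset. Protocol Section 11.4.4.1 describes a "Cox proportional-hazards model with factors for treatment group, region, pubertal status, age, and number of relapses in the year prior to randomization" and has no offset.

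Appendix B of the SAP lists the Cox model as the primary analysis for all three endpoints. Section 2.4.4 sets the status of these analyses: "No confirmative conclusion should be drawn based on p-value because of exploratory nature of open-label period analysis".

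**The concern.** An offset for length of observation belongs in a rate model, where the response is a count and exposure is a separate, known quantity. In a Cox model the observed time is the response. Putting it on the right-hand side conditions each risk set on information from the future, namely how long each member will remain under observation.

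Two things follow. The fitted coefficient is then no longer a log hazard ratio. And when follow-up differs between arms, it can move away from zero even if the hazards are identical. The second case matters here because the open-label period runs to week 192 after randomization, so patients who relapse early in the double-blind period enter earlier and are followed longer (Protocol Section 5.1). If the drug works, that gives the placebo/teriflunomide group more open-label follow-up by design.

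The long-term hazard ratios and confidence intervals in the open-label report are at stake.

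**Working it through.** **Planning figures.** Protocol Section 11.1 and SAP Section 1.3 give 110 and 55 patients, 60% placebo relapse at 2 years, hazard ratio 0.5 and 20% dropout in 2 years.

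- Placebo hazard: −ln(0.4)/2 = 0.4581 per year. Teriflunomide: 0.4581/2 = 0.2291.
- Teriflunomide 2-year relapse: 1 − exp(−2 × 0.2291) = 36.8%, as stated.
- Dropout hazard: −ln(0.8)/2 = 0.1116 per year. A Lachin-Foulkes calculation with this dropout gives N = 167.5, and 79.5% power at 165, consistent with the plan.

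The plan gives no figure for the offset itself.

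**What the offset does.** With offset o_j, the partial likelihood term at event time t_i is

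exp(βx_i + o_i) / Σ_{j at risk} exp(βx_j + o_j).

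With o_j = log T_j, each patient at risk gets weight T_j; with o_j = T_j, weight exp(T_j). Compare two patients both at risk early on, one later followed to week 96 and one to week 192. The second counts 192/96 = 2 times as much under log T. With T in years the factor is exp(96/52) = exp(1.85) = 6.3. An ordinary Cox model weights them equally. Where one arm has longer times, its share of every risk set is inflated and the hazard ratio is pushed down for that arm.

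**Simulation.** 3,000 trials per scenario, exponential times, treatment the only covariate, Lin-Wei robust variance as in Section 2.4.4.1.

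*From randomization:* all 165 patients, placebo moving to the teriflunomide hazard at week 96, follow-up to week 192, 20% dropout per 2 years.

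| Offset | HR | SE of log HR | Rejection of HR = 1 |
|---|---|---|---|
| none | 0.59 | 0.23 | 65% |
| log T | 0.54 | 0.28 (+23%) | 62% |
| T, years | 0.51 | 0.34 (+47%) | 54% |

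Without dropout, 0.61 becomes 0.56 (log T) or 0.53 (T). With a constant true hazard ratio of 0.50 and no crossover, the model without offset returns 0.498; log T gives 0.431 and T in years 0.371.

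*Open-label only, identical hazards in both arms (0.2291 or 0.4581).* Entry is assumed at 8 weeks plus an exponential time at the arm's double-blind hazard, capped at week 96. Mean available follow-up is then:

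- teriflunomide: 192 − 8 − 52 × (1 − exp(−0.2291 × 88/52))/0.2291 = 111 weeks;
- placebo: the same with 0.4581 = 123 weeks.

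| Offset | HR (truth 1.00) | Rejection at nominal 5% |
|---|---|---|
| log T | 1.05 to 1.07 | 4% to 6% |
| T, years | 1.15 to 1.20 | 7% to 8% |

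A wider assumed gap (follow-up capped at 2.6 versus 2.2 years) gives 1.14 with log T and 1.38 with T, the latter with 16% rejection; without offset it is 1.01 with 5.5%.

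*Equal hazards and equal follow-up:* HR 0.99 to 1.01 and rejection 4% to 6% with or without the offset, so no material bias.

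*Disability progression:* with an assumed placebo hazard of 0.06 to 0.12 per year and HR about 0.60, the estimate moves by about 2% to 6%, to between 0.56 and 0.60.

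**The case against.** The best counter-argument is that the sentence in Section 2.4.4.1 is loose English. No other sentence in that description brings time into the Cox model, and the verb could mean only that unequal follow-up is allowed for. Where the SAP wants a true offset, it names the log form and calls it a variable. This is a fair reading of Section 2.4.4.1 alone. It does not carry over to Section 2.4.4.3.2, where the offset is attached to the regression specification itself. Even if only the wording is at fault, a programmer still has to guess, and the same deletion cures it.

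The direction and size also depend on what is guessed. An offset normally enters with coefficient +1. With −log T, the hazard ratio from randomization moves toward 1, from 0.59 to about 0.67, and its standard deviation falls to 0.18 instead of rising. With T in days, the unit implied by the date subtraction in Section 2.4.4.3.2, it is about 0.48 with standard deviation 0.45. So the results for T in years are one case among several, and loss of precision is not universal. Each of these forms still misses the value that the model without offset gives.

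Three further points stand as limits. Under log T the shift from 0.59 to 0.54 is about 0.4 of a standard error. The simulation from randomization used all randomized patients, whereas the efficacy population is those dosed in the open-label period; leaving out double-blind dropouts hardly changes the result (0.60 to 0.54). Switching for high MRI activity was not modelled. Finally, the analyses are exploratory and were not powered. That rules out confirmatory claims, but it does not make a biased estimate acceptable.

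**Conclusion.** The concern holds: the instruction is wrong as written and should be fixed. Followed literally, with the usual positive sign, it turns a relapse hazard ratio of 0.59 from randomization into 0.54 or 0.51. In the open-label-only model it produces 1.05 to 1.20 where the truth is 1.00. Across the forms the text leaves open, one design could yield anything from about 0.48 to 0.67 from randomization.

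These sizes rest on exponential times, the planned hazards, no covariates besides treatment, and an assumed pattern of open-label entry; a different follow-up gap changes the open-label figures. Bias is absent when hazards and follow-up are both equal, and small for rare progression events.

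The scope is limited to the three exploratory Cox models. The confirmatory double-blind analysis is in a separate SAP. The Kaplan-Meier estimates and log-rank tests use no Cox offset, and the annualized relapse rate uses a proper exposure offset in its count model.

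**What to change.** - In SAP Section 2.4.4.1, delete the offset sentence. This also corrects Section 2.4.4.2.1, which inherits it.
- In Section 2.4.4.3.2, delete the offset phrase from the Cox specification.
- Add one sentence saying that time to event or censoring is the Cox response and that unequal follow-up is handled by the censoring rules already written for each endpoint.
- Keep the log-exposure offsets only in the negative binomial models (Section 2.4.4.2.3) and the Poisson model (Section 2.4.4.3.1).

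The cost is two deletions and one sentence. No new data and no extra programming are needed, and no valid analysis is lost.
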